13.4.4 Analyses of Secondary Endpoints and Safety Outcomes

All secondary endpoint analyses will use the ITT sample and will be assessed during the post-transplant follow-up period, which will be a minimum of 12 months.

Separately for each of the secondary incidence endpoints, we will compare the rituximab and control groups on the proportion of patients in each group with at least one episode of the endpoint by estimating the relative risk of the endpoint with its two-sided 90% confidence interval. The absolute risk difference with 90% confidence interval will also be estimated. These methods assume no, or very low rates of, death and re-transplant in the study period. However, if meaningful numbers of subjects have these outcomes, the risk ratio for each incidence endpoint can be estimated through a Cox proportional hazards model with the incidence endpoint as the outcome and right-censoring at death, re-transplant, or other loss to follow-up, following the modeling process described above for the primary endpoint.

Among subjects who are identified as qualifying for and agreeing to participate in the TVI, we will compare the rituximab and control groups on change in standard deviation of tacrolimus levels following the TVI (described in sections 5.3.3 and 8.4) using an analysis of covariance (ANCOVA) model, in which the standard deviation of tacrolimus levels following intervention is the outcome, and study group and pre-intervention standard deviation of tacrolimus levels are the predictors. The group effect with its 90% confidence interval will be estimated.

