Transplant Study Week					4-6																						
Transplant Study Month						2	3	6	9	12	18 ⁶	24 ⁶	25-54 ⁶														
Visit Number		00	01	02	03	04	05	06	07	08	09	10															
	load at post-transplant visits																										
Serology	HIV, HBsAg, HBCAb, HCV Ab (within 12 months of transplant)	X																									
Immunoglobulin Levels	IgG	X	X	X	X	X	X	X	X	X	X	X													X	X	
Pathology	Local Biopsy Histology Scoring (ISHLT), including c1q fixation and C4d			X	X		X	X	X	X	X														X	X	
	Rituximab or Placebo (375 mg/kg)		X	X																							
HUMORAL ANTIBODY CORE – WUSTL (PI: [name])																											
	Serum- Anti-HLA Ab, Non-HLA Ab, Crossmatch Testing	X	X	X	X	X	X	X	X	X	X	X														X	X
	Serum- Autoantibodies	X	X	X	X	X	X	X	X	X	X	X														X	X
MARKERS OF GRAFT INJURY CORE – WUSTL (PI: [name])																											
	Serum- Cytokine/Chemokine/GF				X		X	X	X	X	X	X														X	X
	Bronchoalveolar Lavage (BAL) – Supernatant for Cytokine Analysis		X	X	X		X	X	X	X	X															X	X
MOLECULAR IMMUNOLOGY CORE – ISMMS (PI: [name])																											
	Blood-mRNA Profiling, Gene Exp.				X		X	X	X	X	X	X															
	Bronchoalveolar Lavage – Pellet for Gene Expression Profiles		X	X	X		X	X	X	X	X															X	X
	RNA Sequencing for IgG VDJ Regions ([name], Emory)							X	X	X	X																
CELLULAR IMMUNOLOGY CORE – ISMMS (PI: [name])																											
	Blood- T and B Cell Phenotyping (Flow Cytometry)	X			X		X	X		X	X																X
	Bronchoalveolar Lavage –in Cell Preservative: Phenotyping B Cells		X	X	X		X	X	X	X	X															X	X
	T Cell Function (ELISPOT) and Plasma to Archive	X						X		X	X																X
IMMUNOHISTOCHEMISTRY CORE –ISMMS (PI: [name])																											
	Immunohistochemistry: CD4, FoxP3, CD20 and CD8, CD20 and CD68: (5 unstained slides: Minimum of 3 slides prepared with 2 sections each representative of more than one tissue section)			X	X		X	X	X	X	X															X	X
VIRAL DETECTION CORE –WUSTL (PI: [name])																											
	Bronchoalveolar Lavage – Whole specimen for Viral Detection		X	X	X		X	X	X	X	X															X	X
	Nasal Swab-Viral PCR		X	X	X		X	X	X	X	X															X	X
	Whole Blood Quantitative Viral Studies (CMV/EBV)	X	X	X	X	X	X	X	X	X	X	X														X	X

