7.4. Secondary Mechanistic Endpoints

The following mechanistic endpoints will be assessed using the ITT sample:

- Incidence and kinetics of DSA and autoantibodies, specifically Collagen V (CoIV) and κ 1T
- Frequency, kinetics, phenotype and function of peripheral B cells
- Frequency, kinetics and cytokine profiles of allo and auto-reactive T cells
- Incidence and quantity of B cells and B cell proximity to other cells in the graft tissue

We will correlate pre and/or post-transplant serum reactivity to each autoantigen and to donor HLA with our primary endpoint to prospectively and independently test the hypothesis that autoantibodies can be used as predictors of incipient injury. We will also correlate the presence of serum antibodies with positive C4d staining of the graft tissue (to be collected as part of the clinical component of the study).

To test the hypothesis that rituximab prevents induction of de novo autoantibodies and or DSA, we will compare titers of autoantibodies (or DSA) between the rituximab and control groups. Development of antibodies to either DSA or self-antigens or both and the kinetics of antibody development (time course following transplantation) will be correlated with clinical evidence of AMR and BOS as determined in the clinical part of study described above and the ISHLT criterion. While the absolute numbers of patients in each group with preexisting autoantibodies or DSA is anticipated to be small (thus limiting power) we will compare and report pre vs post-transplant titers in each case to determine if rituximab impacts preexisting antibody.

The results will be analyzed for development of PGD, development of DSA, diagnosis of AMR and BOS. In addition we will also determine any correlation which may exist between the strength of antibodies detected for DSA, HLA and each antibody to self-antigens either alone or cumulatively and clinical outcomes such as PGD, AMR and BOS.

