We will analyze DSA and each type of antibody separately. The DSA and autoantibody data will consist of binary (positive/negative) or ordinal (negative/weak positive/strong positive) responses measured repeatedly at scheduled and unequally spaced intervals. With these features of the data and at this sample size, it may not be feasible to obtain estimates of treatment effect at each time-point using a single statistical model with rituximab and time main effects and their interaction as covariates. Therefore, we will describe the treatment effect over the course of the follow-up period.

The hazard ratio for the association between development of antibodies and clinical outcomes (the endpoint and its components, and the secondary incidence endpoints) will be estimated with its 90% confidence interval using a Cox proportional hazard model with presence or absence of antibodies as time-dependent repeated measures covariates, stratified by treatment group. We will model the association of each antibody on each outcome separately and in combination.

As permitted by the data, we will estimate odds ratios with 90% confidence intervals for the associations between each of the various serum antibodies and C4d staining of the graft tissue. We will estimate these odds ratios at each time point between each pair of antibodies and each antibody and C4d result, both cross-sectional, and cumulative, in which case we would treat any subject with a current or prior positive result as positive for that particular antibody.

Immunophenotyping of B cell and T cell subsets from flow cytometry will be examined. B cell and T cell fractions will be compared between treatment groups within a repeated measures mixed model framework while utilizing samples from the pre-transplant, weeks 4-6, and months

3, 6, 12 and 18 time points. P-values from Tukey's HSD test will be reported to account for multiple comparisons of the mean cell fractions between groups at the various time points.

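### SAP 7.4 names no adjustment for the pre-transplant value in the B- and T-cell mixed model; read naturally, the arm comparisons stay valid but forgo a fraction rho squared of attainable precision

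*SAP*

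**What the plan says.** For the flow-cytometry data, SAP 7.4 compares the cell fractions of the two arms "within a repeated measures mixed model framework while utilizing samples from the pre-transplant, weeks 4-6, and months"; the list goes on to name four months (3, 6, 12 and 18), which makes six time points in all. Tukey HSD p-values are to cover "multiple comparisons of the mean cell fractions between groups at the various time points". The population is set at the head of the section: "The following mechanistic endpoints will be assessed using the ITT sample".

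The text gives no fixed effects, baseline covariate, baseline constraint or covariance structure. It does not say whether the contrast is a visit mean or a change. For the antibody data, the same section does mention a parameterisation, with an arm effect, a time effect and their interaction. That form leaves the arm means free at baseline.

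The six SAP time points match the row "Blood- T and B Cell Phenotyping (Flow Cytometry") in Protocol Appendix 1, whose first sample is at visit 00. Protocol 8.2 allows pre-transplant blood to be taken up to 60 days before surgery. Protocol 8.3 places randomisation after transplant, within 12 hours of the return to the ICU.

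For a different endpoint, the tacrolimus standard deviation, Protocol 13.4.4 plans an ANCOVA in which "study group and pre-intervention standard deviation of tacrolimus levels are the predictors". SAP 7.3.1 analyses that endpoint with a paired t-test instead.

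**The concern.** The pre-transplant sample precedes both randomisation and study drug, so the true arm means at that visit are equal and any observed difference is chance. If that visit has its own arm difference, two things follow. The model estimates a contrast with no treatment effect to find. And with complete data each later contrast is simply the difference in raw visit means, so a value that has been collected and that treatment cannot have changed contributes nothing to precision.

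The fractional loss does not depend on sample size, but it matters more with about 25 children per arm. Protocol 13.6 regards the feasible sample as limited and 35 per arm as probably out of reach, so precision cannot easily be bought with more patients. Not every child reaches month 18 (Appendix 1, footnote 6), so that visit will be smaller still. These comparisons are one part of the evidence for secondary objective 1, the effect of rituximab on post-transplant immunity.

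**Working it through.** Neither document gives a power, standard error, SD or correlation for this comparison, so there is no planned figure to reproduce.

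**Inputs**
- 50 randomised 1:1, hence n = 25 per arm (Protocol 3.1).
- Six visits, one pre-transplant and five post-transplant (SAP 7.4).
- Assumptions: SD standardised to 1, complete data, compound symmetry, the same rho in both arms. Power uses two-sided alpha 0.05 with no multiplicity adjustment.

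**Formulas for the variance of the arm difference at one post-transplant visit**
- Arm means free at every visit: 2/n = 2/25 = 0.0800, whatever rho is.
- Common pre-transplant mean, or pre-transplant value as covariate: (1 − rho²) × 2/n.
- Share of attainable precision forgone: 1 − (1 − rho²) = rho².

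Generalised least squares for the six-visit model gives the same values:

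| rho | Variance, free baseline | Variance, common baseline | Precision forgone | SE, common baseline | Power for 0.6 SD, common baseline |
|---|---|---|---|---|---|
| 0 | 0.0800 | 0.0800 | 0% | 0.283 | 56% |
| 0.3 | 0.0800 | 0.0728 | 9% | 0.270 | 60% |
| 0.5 | 0.0800 | 0.0600 | 25% | 0.245 | 69% |
| 0.7 | 0.0800 | 0.0408 | 49% | 0.202 | 84% |
| 0.9 | 0.0800 | 0.0152 | 81% | 0.123 | >99% |

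With a free baseline the SE is 0.283 and the power 56% in every row. At rho 0.5 the gain is worth 25/0.75 = 33 children per arm.

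**Cost of estimating the slope.** In a simulation of ANCOVA with 25 per arm (20,000 replicates), the gain is 7%, 23% and 48% at rho 0.3, 0.5 and 0.7. The penalty is therefore about 2 percentage points or less.

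**Baseline predictive in the placebo arm only.** Take rho 0.7 under placebo and 0 under rituximab, with a pooled slope.
- Equal SDs: simulated variance falls from 0.0805 to 0.0722, a gain of 10%.
- Rituximab SD 0.2 of placebo: it falls from 0.0406 to 0.0322, a gain of 21%.

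**Multiplicity family.** SAP 7.4 does not say which set of means Tukey's HSD covers. If it is all 12 arm-by-visit means (66 pairs), the critical value is about 3.30 at an assumed 48 × 5 = 240 degrees of freedom. Bonferroni over five post-transplant arm contrasts needs 2.60.

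**The case against.** The strongest reply is that SAP 7.4 is silent rather than wrong. A model with a common baseline mean also keeps the pre-transplant value in the outcome vector and uses exactly the samples listed, so the wording is compatible with the better analysis. This stands: the text does not fix the parameterisation, and a free baseline is the natural reading, not a stated choice.

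The size is also uncertain. Rho is not in the documents, and several features could make it low: marked B-cell depletion with repopulation over 3 to 6 months (Protocol 2.2), Thymoglobulin for every child (7.1.1.1), and a baseline sample that may be 60 days old. This stands too, and is why the placebo-only case is shown.

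A reader might infer stronger things that the documents do not support:
- **That up to half the precision is thrown away.** 49% is only the value at rho 0.7. It is neither a bound nor an expected value.
- **That every interval would narrow.** At rho near zero nothing is gained and a little is lost in degrees of freedom. SAP 7.4 also plans p-values here, not intervals.
- **That the planned comparison is biased.** Under randomisation the unadjusted contrast is valid, and its standard error already covers chance imbalance.
- **That the ANCOVA in Protocol 13.4.4 sets a precedent the SAP breaks only here.** The SAP drops ANCOVA for that endpoint as well.
- **That secondary objective 1 rests on this model.** Antibodies, T-cell function and graft-tissue B cells also serve it.

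The powers above ignore the Tukey adjustment, so they illustrate the gain and do not describe the planned test.

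**Conclusion.** The point holds as a matter of efficiency and of an unstated model, not of validity. On the natural reading, the post-transplant arm comparisons are valid but forgo rho squared of the precision that the samples could give: about 9%, 25% and 49% at assumed correlations of 0.3, 0.5 and 0.7, and close to nothing at low rho. If baseline predicts only in the placebo arm (0.7 against 0), the figure is roughly 10% to 21%. All of these rest on complete data and a rho that the documents do not give; the main series also assumes equal SDs and one rho in both arms. The change is worth making because the baseline is already collected, cannot have been affected by treatment, and costs almost nothing to use.

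**What to change.** In SAP 7.4, keep the same mixed model and the same six samples, and add one sentence with three parts:

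1. The arms share a common pre-transplant mean (fixed effects: time, plus arm by post-transplant time). Alternatively, the pre-transplant fraction enters as a covariate with a visit interaction.
2. Arm differences are estimated only at weeks 4-6 and months 3, 6, 12 and 18.
3. Those five contrasts, for each cell fraction, are the multiplicity family.

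The common-mean form has the advantage of keeping children whose pre-transplant sample is missing. The choice should be fixed before unblinding. The cost is one SAP sentence and a small change in model code, with no new data. If rho turns out to be near zero, the loss in degrees of freedom is negligible.

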9.4.1. Peripheral Blood B cell Phenotyping

Peripheral blood phenotyping will be performed using standardized panels of antibodies (8 color). The efficacy of Rituxan® on peripheral blood CD20 positive B-cells will be assessed using flow cytometry in samples obtained at visit 03 (4-6 weeks post-transplant). The B cell phenotypes to be analyzed and a representative flow cytometry plot illustrating the proposed approach is included as **Table 12** and **Figure 10**.

Table 12: B-cell phenotypes

B cell Subset		Surface Phenotype	
Transitional	T1-T2	IgD+CD27- MTG+CD24hi CD38hi	
	T3	IgD+CD27- MTG+CD24int CD38int	
Naïve		IgD+CD27- MTG-CD24int CD38int	
Memory	Unswitched	IgD+ CD27+	
	Switched	Resting	IgD-CD27+CD21+CD95-CD24+
		Activated	IgD-CD27+CD21-CD95+CD24-
Switched CD27- memory (DN)		IgD-CD27-CD21+CD95-	
Antibody secreting cells	Plasmablasts	IgD-CD27++CD38++CD19+	
Autoimmune phenotype		CD19+, CD11c+ CD220+	

Figure 10: B cell phenotypes flow cytometry

B cell phenotyping will be performed along with analyses of T cells and APCs (see below). The team will quantify total B cells, naïve and memory B cells, plasma cells, transitional cells, B cells with an active “autoimmune” phenotype and Breg using the panels depicted in Table 7.^{52,94,95} Kinetic analysis will be performed for each patient and differences between the treatment group and the control group will be determined.

Antigen specificity analyses will focus on autoantigenic B cells reactive to ColV and Ka1T. Fluorescent labeled pentamers of ka1T using the recombinant ka1T produced in our lab will be used to identify the number of B cells specific for ka1T and their correlation with circulating Abs to ka1T and other self-Ags (ColV) will be analyzed.

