13.4 Analysis Plan

The overall focus of our statistical analysis of the clinical portion of the study will be on the estimation of hazard ratios (HR) and risk ratios (RR) and their two-sided 90% confidence intervals comparing the rituximab and placebo groups on each endpoint of the study. Focusing on estimates and confidence intervals will allow us to assess the range potential efficacies as best we can within the limitations imposed by studying such a rare pediatric population.

Further detail describing the analysis plan will be contained in a Statistical Analysis Plan (SAP) that will be maintained by the SACCC and updated as necessary.

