1. PROTOCOL SYNOPSIS

Title	B cell Targeted Induction to Improve Outcomes in Pediatric Lung Transplantation
Clinical Phase	Phase 2
Number of Sites	7 US Sites
IND Sponsor/Number	NIAID/IND Number 121403
Primary Study Objective	To determine whether rituximab induction along with standard of care immunosuppression will improve outcomes following pediatric lung transplantation.
Secondary Study Objectives	
 1. To determine the effects of rituximab induction on post-transplant immunity in pediatric lung transplant recipients. 2. To assess the safety and tolerability of rituximab. 3. To assess the feasibility of a phone based intervention to decrease tacrolimus trough level variability.
Study Design/Treatment Description	Phase 2, prospective, multi-center, double-blind, randomized, placebo-controlled clinical trial in which 50 primary pediatric lung transplant recipients will be randomized (1:1) to receive either induction therapy with anti-CD20 mAb (375 mg/m ²) IV or placebo (IV day 0 and day 12 post-transplant) plus standard of care immunosuppression (thymoglobulin induction, tacrolimus or generic equivalent, MMF or generic equivalent, and steroids).
Primary Endpoint	
The primary endpoint is a composite of the earliest time to any of the following events during the follow-up period:
 
 • Chronic Allograft Dysfunction • Listed for Retransplant • Death
Secondary Clinical Endpoints	
 1. Post-transplant clinical outcomes including: 
 a. Incidence of chronic allograft dysfunction, listing for retransplantation, and death during the follow-up period, which will be a minimum of 12 months post-transplant b. Incidence of Primary Graft Dysfunction c. Incidence of Grade A Acute Rejection during the follow-up period, which will be a minimum of 12 months post-transplant d. Incidence of Antibody Mediated Rejection during the follow-up period, which will be a minimum of 12 months post-transplant e. Incidence of tacrolimus variability threshold during the follow-up period, which will be a minimum of 12 months f. Percentage of participants meeting tacrolimus variability threshold who complete tacrolimus variability intervention

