6.2. Treatment Adherence

Treatment Groups:

- **Rituximab Group** – induction therapy with anti-CD20 mAb (375 mg/m²) IV on day 0 and day 12 post-transplant plus standard of care immunosuppression (thymoglobulin induction, tacrolimus or equivalent, MMF or equivalent, and steroids).
- **Placebo Group** – induction therapy with placebo IV on day 0 and day 12 post-transplant plus standard of care immunosuppression (thymoglobulin induction, tacrolimus or equivalent, MMF or equivalent, and steroids).

Randomization to one of the two groups will occur once the subject has received the transplant and is deemed hemodynamically stable. The first infusion must be administered within 12 hours of returning to the ICU following transplant. The second infusion should be administered on day 12 (\pm 2 days) post-transplant.

Adherence will be summarized for the ITT sample. The status of each infusion will be classified as complete, partial, or not done and the duration (or extent) of exposure will be calculated by determining the number of days between first and second infusions (+1) for each subject in the

sample. These variables will then be summarized using appropriate statistics in a table and subject-level details will be presented in a listing.

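### Tukey's HSD is ill-suited to the between-group comparisons of B- and T-cell fractions: over all 12 group-by-time means it over-corrects, and the SAP names neither the contrasts nor the alpha

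*SAP*

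**What the plan says.** SAP 7.4 (Secondary Mechanistic Endpoints) states that "B cell and T cell fractions will be compared between treatment groups within a repeated measures mixed model framework", "utilizing samples from the pre-transplant, weeks 4-6, and months" "3, 6, 12 and 18 time points". That makes six time points: one before transplant and five after. The multiplicity statement is that p-values from Tukey's "HSD test will be reported to account for multiple comparisons of the mean cell fractions between groups at the various time points".

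The section does not say whether Tukey is run over all group-by-time means or separately at each time. It gives no alpha, no list of contrasts and no statement about the several cell subsets. The protocol's statistical section names no multiplicity method for this analysis. On what is to be compared, Protocol 9.4.1 says: "Kinetic analysis will be performed for each patient and differences between the treatment group and the control group will be determined".

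On timing, SAP 6.2 says: "Randomization to one of the two groups will occur once the subject has received the transplant and is deemed hemodynamically stable". The pre-transplant flow cytometry sample is Visit 00 in Protocol Appendix 1, so it precedes both randomisation and study drug.

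**The concern.** The sentence names its own family: comparisons between groups, at each of several times. Tukey's HSD is built for a different family, namely all pairwise differences among a set of means. Most pairs among 12 group-by-time means compare one arm with itself at two times, or one arm at one time with the other arm at another. The correction pays for those pairs although the sentence does not ask for them. If the procedure is instead run within a time point there are only two means, and nothing is corrected.

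These measurements are named secondary mechanistic endpoints and serve the first secondary objective. With about 25 patients per arm, an unnecessary loss of precision matters. So does the open choice. A raw p of 0.01 becomes about 0.27 to 0.29 over 12 means (48 to 200 degrees of freedom) and stays 0.01 within a time point, and the text does not say explicitly which was meant.

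**Working it through.** The plan gives no number of comparisons, critical value or power for this analysis, so there is no figure to reproduce.

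**Inputs from the documents.** Two arms; "50 primary pediatric lung transplant recipients will be randomized (1:1) to receive" one of them, so 25 + 25; six time points.

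**Assumptions.** Alpha is not stated for these p-values. Both 5% and 10% are shown; 10% would match the protocol's "two-sided 90% confidence intervals comparing the rituximab and placebo groups on each endpoint of the study" (Protocol 13.4). Degrees of freedom are taken as 48 (two groups of 25) and 200 (a mixed model borrowing across visits). Effect sizes and within-subject correlations are also assumed.

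**Count of pairs.** 2 x 6 = 12 means; 12 x 11 / 2 = 66 pairs.
- Between arms, same time: 6, of which 5 are post-randomisation.
- Same arm, different times: 2 x 15 = 30.
- Different arms, different times: 30.

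**Critical values for |t|.** Tukey: studentized-range quantile (1 - alpha; 12 means, df) / sqrt(2). Bonferroni over m contrasts: t quantile at 1 - alpha/(2m).

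| Alpha | df | Tukey, 12 means | Bonferroni, 5 | Ratio | Bonferroni, 6 | Ratio |
|---|---|---|---|---|---|---|
| 5% | 48 | 3.434 | 2.682 | 1.28 | 2.752 | 1.25 |
| 5% | 200 | 3.307 | 2.601 | 1.27 | 2.665 | 1.24 |
| 10% | 48 | 3.150 | 2.407 | 1.31 | 2.481 | 1.27 |
| 10% | 200 | 3.058 | 2.345 | 1.30 | 2.414 | 1.27 |

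Limits are therefore 27-31% wider than for five contrasts, and 24-27% wider than for six. The ratio does not depend on sample size.

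**Error under the 12-mean reading.** In a simulation (20,000 runs, 25 per arm, within-subject correlation 0 to 0.7), family-wise error over the five contrasts was 0.5-0.7% at nominal 5% and 1.1-1.4% at nominal 10%. This is well inside the nominal level.

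**Power.** Take the noncentrality that gives 80% (or 90%) power at the five-contrast Bonferroni limit, then find the power of the same contrast at the Tukey limit from the noncentral t. At 5% and 48 df, noncentrality 3.54 gives 80% and falls to 54.7%; noncentrality 4.00 gives 90% and falls to 70.8%. Over the four alpha and df combinations the results are 55-56% and 71-72%.

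Noncentrality is d / sqrt(2/25), with d the difference in SD units, so 80% power corresponds to d of about 1. At 5% and 48 df:
- d = 1.5: 96% under Tukey against 99% under Bonferroni over five.
- d = 2: above 99.9% under both.

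**Within-time reading.** Two means make one pair. Studentized range (95%; 2, 48) / sqrt(2) = 2.011, which is t(97.5%; 48) = 2.011, so there is no adjustment. Over five times, if independent, family-wise error is 1 - 0.95^5 = 22.6% at 5% and 1 - 0.90^5 = 41.0% at 10%. Simulated with within-subject correlation 0.7 to 0.3, it is 15-21% and 28-38%.

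**The case against.** A reader might infer that the planned test is invalid, or that false positives run at 23%. The documents do not support that. Over the 12 means Tukey does account for the between-group comparisons, conservatively. The 23% needs the within-time reading, which sits badly with a sentence whose purpose is to account for multiple comparisons, and it also needs independence across visits. The charge that stands is poor fit and incomplete specification.

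A second objection is that change over time is itself of interest: the endpoint includes kinetics, and the protocol plans a kinetic analysis for each patient. If the 30 same-arm pairs are added to the 6 between-arm pairs, Bonferroni over 36 contrasts at 5% and 48 df has a limit of 3.39, against Tukey's 3.43, and the penalty almost vanishes. That is correct for that family. But the Tukey sentence limits itself to comparisons between groups, and the family it names is the one used here.

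Third, rituximab is expected to deplete B cells markedly, so differences may be large and the power loss small. This stands for effects of 2 SD or more. The documents give no effect size, and the same sentence also covers T-cell fractions and all later visits.

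Fourth, a reader might infer that the SAP treats the pre-transplant value as an outcome and omits baseline adjustment. The text does not go that far: it lists the sample among those used and leaves the model terms unspecified. Keeping baseline in the response vector is a recognised choice. What stands is only that a between-arm test at that time cannot show a treatment effect.

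Finally, Protocol Tables 12 and 13 list about 15 subsets. Adjusting over five times within each subset leaves multiplicity across subsets open. That is true, and the report should say so.

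**Conclusion.** The concern holds as a matter of efficiency and specification. For the family that SAP 7.4 itself names, Tukey over the 12 means is valid but over-corrects: limits are about 27-31% wider than needed for the five post-randomisation contrasts, and power falls from 80% to about 55% or from 90% to about 71%. For very large effects the loss is negligible. The within-time reading would leave error across visits uncontrolled, but it is the less natural one.

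The size rests on assumed alpha (5% or 10%) and degrees of freedom (48 to 200), with Bonferroni as the comparator. The conclusion does not change across those ranges, or if all six same-time contrasts are kept. This is a secondary mechanistic analysis, and the primary endpoint is not touched. The change is worth making because it is nearly free.

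**What to change.** Replace the Tukey sentence in SAP 7.4 by:

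> Treatment groups are compared at weeks 4-6 and months 3, 6, 12 and 18 (five contrasts per cell subset) in the mixed model, adjusted for the pre-transplant value; p-values are adjusted over these five contrasts by Holm, at alpha = [value to be stated]. No treatment test is made at the pre-transplant time. Within-arm changes over time are descriptive, and no adjustment is made across cell subsets, which will be stated in the report.

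Holm is never less powerful than the Bonferroni limits used above and needs no assumption about correlation between visits. The cost is one SAP sentence and the matching line of code, with no new data and nothing for patients. The small downside is that comparisons over time within an arm are no longer covered by the adjustment.
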